| | 
Grade 2
 | 
For Grade 2: Hold study drug/study regimen dose until resolution to Grade ≤ 1. -Permanently discontinue study drug/study regimen if it does not resolve to Grade ≤ 1 within 30 days or if there are signs of respiratory insufficiency.
 | 
For Grade 2:
 
 - Monitor symptoms daily and consider hospitalization. - Obtain Neurology consult, and initiate evaluation. - Consider, as necessary, discussing with the Clinical Study Lead. - If clinical course is rapidly progressive (particularly if difficulty breathing and/or trouble swallowing), promptly start IV methylprednisolone 2 to 4 mg/kg/day systemic steroids along with receiving input from Neurology consultant - If clinical course is not rapidly progressive, start systemic steroids (e.g., prednisone 1 to 2 mg/kg/day PO or IV equivalent); if no improvement within 2 to 3 days, continue additional work up and start treatment with IV methylprednisolone 2 to 4 mg/kg/day - If after start of IV methylprednisolone at 2 to 4 mg/kg/day there is no improvement within 2 to 3 , consider starting another immunosuppressive therapy such as TNF inhibitors (e.g., infliximab at 5 mg/kg IV, may be repeated at 2 and 6 weeks after initial dose at the discretion of the treating provider or relevant practice guidelines). Caution: It is important to rule out sepsis and refer to infliximab label for general guidance before using infliximab. |
| | 
Grade 3 or 4
 | 
For Grade 3: Hold study drug/study regimen dose until resolution to Grade ≤ 1. Permanently discontinue study drug/study regimen if Grade 3 imAE does not resolve to Grade ≤ 1 within 30 days or if there are
 | 
For Grade 3 or 4 (severe or life-threatening events):
 |

| | | | |
|--|--|--|--|
| | | 
signs of respiratory insufficiency.
 
For Grade 4: -Permanently discontinue study drug/study regimen.
 | 
 - Monitor symptoms closely; recommend hospitalization. - Obtain Neurology consult. - Consider, discussing with the Clinical Study Lead as needed. - Promptly start IV methylprednisolone 2 to 4 mg/kg/day systemic steroids along with receiving input from Neurology consultant. - If after start of IV methylprednisolone at 2 to 4 mg/kg/day there is no improvement within 2 to 3days, consider starting another immunosuppressive therapy such as TNF inhibitors (e.g., infliximab at 5 mg/kg IV, may be repeated at 2 and 6 weeks after initial dose at the discretion of the treating provider or relevant practice guidelines). Caution: It is important to rule out sepsis and refer to infliximab label for general guidance before using infliximab. - Consider whether patient may require IV IG, plasmapheresis. |
|--|--|--|--|

AE Adverse event; CTC Common Toxicity Criteria; CTCAE Common Terminology Criteria for Adverse Events; imAE immune-mediated adverse event; IV intravenous; NCI National Cancer Institute; PO By mouth.

Dosing Modification and Toxicity Management Guidelines for Immune-mediated, Infusion Related, and Non Immune-mediated Reactions for Durvalumab Monotherapy

Table 1- Other – Immune- Mediated Reactions

| Severity Grade of the Event (NCI CTCAE version 4.03) | Dose Modifications | Toxicity Management |
|--|--|--|
| Any Grade | 
General Guidance
 
Note: It is possible that events with an inflammatory or immune mediated mechanism could occur in nearly all organs, some of them are not noted specifically in these guidelines (e.g. immune thrombocytopenia, haemolytic anaemia, uveitis, vasculitis).
 | 
 - The Clinical Study Lead may be contacted for immune-mediated reactions not listed in the “specific immune-mediated reactions” section - Thorough evaluation to rule out any alternative etiology (e.g., disease progression, concomitant medications, and infections) - Consultation with relevant specialist - Treat accordingly, as per institutional standard. |
| Grade 1 | No dose modifications. | 
 - Monitor as clinically indicated. |
| Grade 2 | 
Hold study drug/study regimen until resolution to ≤Grade 1 or baseline.
 
 • If toxicity worsens, then treat as Grade 3 or Grade 4. • Study drug/study regimen can be resumed once event stabilizes to Grade ≤1 after completion of steroid taper. • Consider whether study drug/study regimen should be permanently discontinued in Grade 2 events with high likelihood for morbidity and/or mortality when they do not rapidly improve to Grade <1 upon treatment with systemic steroids and following full taper | 
 - For Grade 2, 3, or 4 - Treat accordingly, as per institutional standard, appropriate clinical practice guidelines, and society guidelines - (e.g., NCCN, ESMO) |

| | | |
|---|--|--|
| Grade 3 | Hold study drug/study regimen | |
| Grade 4 | Permanently discontinue study drug/study regimen | |
| Dosing Modification and Toxicity Management Guidelines for Immune-mediated, Infusion Related, and Non Immune-mediated Reactions for Durvalumab Monotherapy | | |
| Table 2- Infusion-Related Reactions | | |
| Severity Grade of the Event (Refer to NCI CTCAE applicable version in study protocol for defining the CTCAE grade/severity) | Dose Modifications | Toxicity Management |
| Any Grade | General Guidance | 
 - Management per institutional standard at the discretion of investigator - Monitor patients for signs and symptoms of infusion-related reactions (e.g., fever and/or shaking chills, flushing and/or itching, alterations in heart rate and blood pressure, dyspnea or chest discomfort, skin rashes etc.) and anaphylaxis (e.g., generalized urticaria, angioedema, wheezing, hypotension, tachycardia, etc.) |
| Grade 1 | The infusion rate of study drug/study regimen may be decreased by 50% or temporarily interrupted until resolution of the event | 
For Grade 1 or Grade 2:
 
 - Acetaminophen and/or antihistamines may be administered per institutional standard at the discretion of the investigator - Consider premedication per institutional standard prior to subsequent |

| | | |
|------------------|---|---|
| Grade 2 | 
The infusion rate of study drug/study regimen may be decreased 50% or temporarily interrupted until resolution of the event
 
Subsequent infusions may be given at 50% of the initial infusion rate
 | 
doses
 
 - Steroids should not be used for routine premedication of \leqGrade 2 infusion reactions |
| Grade 3/4 | 
Permanently discontinue study drug/study regimen
 | 
For Grade 3 or 4:
 
Manage severe infusion-related reactions per institutional standard appropriate clinical practice guidelines and society guidelines.
 |

Dosing Modification and Toxicity Management Guidelines for Immune-mediated, Infusion Related, and Non Immune-mediated Reactions for Durvalumab Monotherapy

Table 3- Non-immune Mediated Reactions

| Severity Grade of the Event (NCI CTCAE version 4.03) | Dose Modification | Toxicity Management |
|--|--|---|
| Any Grade | Note: dose modifications are not required for adverse events not deemed to be related to study treatment (i.e. events due to underlying disease) or for laboratory abnormalities not deemed to be clinically significant. | Treat accordingly as per institutional standard |
| 1 | No dose adjustment | Treat accordingly as per institutional standard |
| 2 | Hold study drug/study regimen until resolution to ≤ Grade 1 or baseline | Treat accordingly as per institutional standard |
| 3 | Hold study drug/study regimen until resolution to ≤ Grade 1 or baseline For AEs that downgrade to ≤ Grade 2 within 7 days or resolve to ≤ Grade 1 or baseline within 14 days, resume study drug/study regimen administration. Otherwise, discontinue study drug/study regimen | Treat accordingly as per institutional standard |
| 4 | Discontinue Study drug/study regimen (Note for Grade 4 labs, decision to discontinue would be based on accompanying clinical signs/symptoms and as per Investigator’s clinical judgment and in consultation with the sponsor) | Treat accordingly as per institutional standard |

Abbreviations: AChE = acetylcholine esterase; ADA = American Dietetic Association; AE = adverse event; ALP = alkaline phosphatase; ALT = alanine aminotransferase; AST = aspartate aminotransferase; CT = computed tomography; GI = gastrointestinal; IDS=Infectious Disease Service; ILD = interstitial lung disease; IM = intramuscular; irAE = immune-related adverse event; IV = intravenous; NCI CTCAE = National Cancer Institute Common Terminology Criteria for Adverse Events; PO = by mouth; TNF = tumor necrosis factor; TSH = thyroid stimulating hormone; ULN = upper limit of normal.

Note: As applicable, for early phase studies, the following sentence may be added: “Any event greater than or equal to Grade 2, please discuss with the Clinical Study Lead.”

List of Abbreviations

| | | | |
|-----------------|---|----------------|--|
| AChE | Acetylcholinesterase | ILD | Interstitial lung disease |
| ACTH | Adrenocorticotrophic hormone | imAE(s) | Immune-mediated adverse event(s) |
| ALT | Alanine aminotransferase | INR | International normalized ratio |
| ASCO | American Society of Clinical Oncology | IU | International units |
| AST | Aspartate aminotransferase | IV | Intravenous |
| (T) Bili | (Total) Bilirubin | IVIG | Intravenous immunoglobulin |
| BNP | B-type natriuretic peptide | LDH | Lactate dehydrogenase |
| BUN | Blood urea nitrogen | LFTs | Liver function tests |
| CRP | C-reactive protein | LLN | Lower limit of normal |
| CT | Computed tomography | MRCP | Magnetic resonance cholangiopancreatography |
| CTCAE | Common Terminology Criteria for Adverse Events | MRI | Magnetic resonance imaging |
| CTLA-4 | Cytotoxic T-lymphocyte antigen-4 | NCCN | National Comprehensive Cancer Network |
| DILI | Drug-induced liver injury | NCI | National Cancer Institute |
| ECG | Electrocardiogram | PD-L1 | Programmed cell death ligand-1 |
| ECHO | Echocardiogram | PJP | Pneumocystis jirovecii pneumonia |
| ESMO | European Society of Medical Oncology | PO | By mouth |
| GI | Gastrointestinal | SCAR | Severe cutaneous adverse reaction |
| HBcAb | Hepatitis B core antibody | SITC | Society for Immunotherapy of Cancer |
| HBsAg | Hepatitis B envelope antigen | SJS | Stephen Johnson Syndrome |
| HBsAg | Hepatitis B surface antigen | T1DM | Type 1 diabetes mellitus |
| HBV | Hepatitis B virus | T3 | Triiodothyronine |
| HCC | Hepatocellular cancer | T4 | Thyroxine |
| HCV | Hepatitis C virus | TEN | Toxic Epidermal Necrolysis |
| HgA1c | Hemoglobin A1C | TMG(s) | Toxicity management guideline(s) |
| ICI(s) | Immune checkpoint inhibitor(s) | TSH | Thyroid stimulating hormone |
| | | ULN | Upper limit of normal |

Human Research Protections Program Immediate Report Form

The Immediate Reporting Policy that governs what you must report using this form is available at the following web address: http://researchintegrity.weill.cornell.edu/institutional_review_board/irb_policies_and_procedures.html. The policy spans 5 categories: Adverse Events/Unexpected Adverse Device Effects (Section A of this form), Other Risk Reporting (Section B of this form), Protocol Deviation Reporting (Section C of this form) and Other Compliance Reporting (Section D of this form).

If you have any questions, please email [contact] or call [contact].

DIRECTIONS:

- (a) Fill out questions 1 through 8 on this page.
- (b) Then choose the section on this form that corresponds to the type of Immediate Report you are making. Any given section you choose will have only 1 to 7 questions.
- (c) Create a PDF of this form and attach the most current WCMC IRB consent document and any supplemental information.
- (d) Sign this form with Principal Investigator signature on the last page and send to [contact].

NOTE:

- If you are using the Clinical and Translational Science Center (CTSC) you must also CC your Immediate Report to [contact].
- If you are using the Weill Cornell Medical College Data Safety Monitoring Board (WCMC DSMB) you must also CC your Immediate Report to [contact].
- If your protocol is subject to the requirements of the Institutional Biosafety Committee (IBC), you must also CC your Immediate Report to [contact].

1. Principal Investigator:
2. Protocol #:
3. Protocol Title:
4. Brief One Sentence Description of Report (**This will be used to reference this specific submission in all IRB correspondence about this Immediate Report**):
5. Status of Protocol at WCMC Site Open Open, Closed to Subject Accrual Open, Data Analysis Only
6. Funding Source:
7. Does this protocol involve use of FDA-regulated product(s) including those that are FDA-approved? Yes No
 - a. If yes, is this protocol conducted under an IND or IDE? Yes No
 - b. If yes, name IND or IDE sponsor:
8. Check (and email this submission to) all that apply: I use the: WCMC Data Safety Monitoring Board (WCMC DSMB)
 WCMC Institutional Biosafety Committee (IBC) Clinical and Translational Science Center (CTSC)

A: ADVERSE EVENT REPORTING / UNANTICIPATED ADVERSE DEVICE EFFECTS

Tip: The goal of this section is to capture emergent risk information that has an impact on the rights and welfare of WCMC subjects and may also require compliance management.

1. I am reporting (check all that apply):

- Adverse Event that meets all 3 conditions as outlined in Section I(A) of the Immediate Reporting Policy
http://researchintegrity.weill.cornell.edu/institutional_review_board/irb_policies_and_procedures.html.

Adverse Event that requirements for reporting and a death or serious injury due to a defect of a Humanitarian Use Device, as outlined in Section I(C) of the Immediate Reporting Policy
http://researchintegrity.weill.cornell.edu/institutional_review_board/irb_policies_and_procedures.html.

Unanticipated adverse device effect as outlined in Section II(A) of the Immediate Reporting Policy
http://researchintegrity.weill.cornell.edu/institutional_review_board/irb_policies_and_procedures.html.

Describe the adverse event, its cause, and indicate any actions taken to date at the WCMC site to protect the rights and welfare of WCMC research subjects. Provide as much detail as possible. If the PI or any committee/board determines that the Immediate Report requires an amendment to the protocol or consent, the PI has 30 days from the date of making the Immediate Report (or release of the sponsor amendment) to submit a protocol amendment to the IRB. If this requirement cannot be met, a request for an extension must be made.

1. Please explain whether you believe this adverse event suggests that the research places WCMC subjects at a greater risk of harm than was previously known or recognized. If so, include what additional action you intend to take in your management of this change in risk. E.g., Documented contact with subjects by the PI or medically qualified co-I; amendment to protocol or consent).
2. Name any agencies or entities (E.g., FDA, NIH, sponsor, DSMB, etc.) that have been notified of this adverse event.

B: OTHER RISK REPORTING

Tip: The goal of this section is to capture emergent risk information that has an impact on the rights and welfare of WCMC subjects. If none of the below checkboxes apply, submit an acknowledgment submission instead of an Immediate Report.

1. I am reporting (check all that apply):

An interim analysis, safety monitoring report, publication in the literature, or revised Investigator Brochure that indicates an increase in the frequency or magnitude of a given harm, uncovers a new risk, or provides more information about the benefits of the human research.
(PLEASE ATTACH THE ADDITIONAL DOCUMENTATION)

Change in FDA labeling or withdrawal from marketing of a drug, device, or biologic used in the human research protocol.

- Clinical Hold, Enrollment Hold (excluding planned holds for interim analysis), or Study Termination due to Emergent Risk Information
- Complaint of a participant that indicates participants or others might be at increased risk of harm or at risk of a new harm.

2. Please summarize the information and how you intend to manage the new risk posed to WCMC research participants. Include any actions taken to date.

C: PROTOCOL DEVIATIONS

Tip: The sponsor and the IRB are separate and distinct entities with different protocol deviation reporting requirements. Please consult with your sponsor to find out what protocol deviations you must submit to your sponsor. This form is meant to capture protocol deviations that must be reported to the IRB. Note that, if WCMC is the lead/coordinating site, then protocol deviation reports submitted from other sites must be submitted to the WCMC IRB.

1. I am reporting (check all that apply):

- Protocol deviation that was made in order to eliminate an apparent immediate hazard to participants.
- Breach of Confidentiality
- Protocol deviation that represents a failure to follow the protocol or IRB policies and determinations due to the action or inaction of the investigator or research staff. (Exception: Rescheduling of research appointments due to holidays, vacations, accommodation of research subject, etc.) which meets both of the following conditions:
 - a. The deviation has the potential to negatively impact subject safety or integrity of study data (ability to draw conclusions from the study data), or affect the subject's willingness to participate in the study **AND**
 - b. The deviation places WCM subjects **at greater risk of harm** (including physical, psychological, economic or social harm).

2. Did this deviation occur at an external site (non-WCMC research site for which WCMC is the lead/coordinating site)?

- No Yes, answer (a)

a) What is the status of the research protocol at the non-WCMC research site?

Open Open, Closed to Subject Accrual Open, Data Analysis Only

3. Date the Protocol Deviation Occurred:

4. Date the WCMC PI was notified:

5. Describe the protocol deviation and clearly state how this protocol deviation differs from what the IRB-approved protocol and/or IRB policy allows. Include why the deviation occurred. If the deviation occurred because of an error, please assess the root cause of that error.

6. Describe what actions have been taken to date to ensure the rights and welfare of the participant(s).

7. What preventative actions have been taken to ensure this deviation does not reoccur? Note: While some deviations occur due to human error, some represent systemic issues that need to be resolved. If the research staff will be more careful in the future, please help the IRB understand how the research staff will do this.

D: OTHER COMPLIANCE REPORTING

1. I am reporting (check all that apply):

- Finding of noncompliance or allegation of noncompliance
- Complaint of a participant that cannot be resolved by the research team.
- Incarceration of a participant in a protocol not approved to enroll prisoners.

2. Please describe the scenario in detail and indicate any actions taken to date:

WCMC Principal Investigator's Signature _____ Date: _____

IMPORTANT: Before providing your digital signature, combine this form and supporting documents into a single PDF.

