6.0 DOSE DELAYS/DOSE MODIFICATIONS

6.1 Dose Modification and Toxicity Management

Guidelines for the management of immune-mediated reactions, infusion-related reactions, and non-immune-mediated reactions for durvalumab are in the Dosing Modification and Toxicity Management Guidelines in Appendix B. Patients should be thoroughly evaluated and appropriate efforts should be made to rule out neoplastic, infectious, metabolic, toxin, or other etiologic causes of the imAE. Serologic, immunologic, and histologic (biopsy) data, as appropriate, should be used to support an imAE diagnosis. In the absence of a clear alternative etiology, events should be considered potentially immune related. In addition, there are certain circumstances in which durvalumab should be permanently discontinued (see section 5.4.1 and the Dosing Modification and Toxicity Management Guidelines in Appendix B).

Following the first dose of durvalumab, subsequent administration of durvalumab can be modified based on toxicities observed as described in the Dosing Modification and Toxicity Management Guidelines in APPENDIX B. Dose reductions are not permitted. Based on the mechanism of action of durvalumab leading to T-cell activation and proliferation, there is the possibility of observing immune related Adverse Events (irAEs) during the conduct of this study. Potential irAEs include immune mediated enterocolitis, dermatitis, hepatitis, and endocrinopathies. Subjects should be monitored for signs and symptoms of irAEs. In the absence of an alternate etiology (e.g., infection or PD) signs or symptoms of enterocolitis, dermatitis, hepatitis, and endocrinopathy should be considered to be immune-related.

Dose modification recommendations and toxicity management guidelines for immune-mediated reactions, for infusion-related reactions, and for non-immune-mediated reactions are detailed in Appendix B, Tables 1, 2, and 3 respectively.

In addition, management guidelines for adverse events of special interest (AESIs) are detailed in Appendix B, Table 1. All toxicities will be graded according to NCI CTCAE v4.03.

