6.2.4 Excluded Concomitant Medications

The following medications are considered exclusionary during the study.

1. Any investigational anticancer therapy other than the protocol specified therapies
2. mAbs against CTLA-4, PD-1, or PD-L1 other than those under investigation in this study.
3. Any concurrent chemotherapy, radiotherapy, immunotherapy, biologic or hormonal therapy for cancer treatment, other than the protocol specified therapy. Concurrent use of hormones for noncancer-related conditions (e.g., insulin for diabetes and hormone replacement therapy) is acceptable.
4. Immunosuppressive medications including, but not limited to systemic corticosteroids at doses not exceeding 10 mg/day of prednisone or equivalent, methotrexate, azathioprine, and TNF- α blockers. Use of immunosuppressive medications for the management of investigational product-related AEs or in subjects with contrast allergies is acceptable. In addition, use of inhaled and intranasal corticosteroids is permitted. A temporary period of steroids will be allowed if clinically indicated and considered to be essential for the management of non-immunotherapy related events experienced by the patient (e.g., chronic obstructive pulmonary disease, radiation, nausea, etc).
5. Live attenuated vaccines within 30 days of durvalumab dosing (i.e., 30 days prior to the first dose, during treatment with durvalumab and for 30 days post discontinuation of durvalumab). Inactivated viruses, such as those in the influenza vaccine, are permitted.
6. EGFR TKIs should not be given concomitantly and should be used with caution in the 90 days post last dose of durvalumab. Increased incidences of pneumonitis (with third generation EGFR TKIs) and increased incidence of transaminase increases (with 1st generation EGFR TKIs) has been reported when durvalumab has been given concomitantly.
7. Herbal and natural remedies which may have immune-modulating effects.

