7.1.11 Nephritis

Consult with Nephrologist. Monitor for signs and symptoms that may be related to changes in renal function (e.g. routine urinalysis, elevated serum BUN and creatinine, decreased creatinine clearance, electrolyte imbalance, decrease in urine output, proteinuria, etc). Patients should be thoroughly evaluated to rule out any alternative etiology (e.g., disease progression, infections etc.). Steroids should be considered in the absence of clear alternative etiology even for low grade events (Grade 2), in order to prevent potential progression to higher grade event. Guidelines for the management of patients with immune-mediated neurotoxic events are provided in Table 1.

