APPENDIX B
DOSING MODIFICATIONS AND TOXICITY MANAGEMENT GUIDELINES
Tables 1, 2 and 3

General Considerations Regarding Immune-Mediated Reactions

These guidelines are provided as a recommendation to support investigators in the management of potential immune-mediated adverse events (imAEs).

Immune-mediated events can occur in nearly any organ or tissue, therefore, these guidelines may not include all the possible immune-mediated reactions. Investigators are advised to take into consideration the appropriate practice guidelines and other society guidelines (e.g., National Comprehensive Cancer Network (NCCN), European Society of Medical Oncology (ESMO)) in the management of these events. Refer to the section of the table titled “Other -Immune-Mediated Reactions” for general guidance on imAEs not noted in the “Specific Immune-Mediated Reactions” section.

Early identification and management of imAEs is essential to ensure safe use of the study drug. Monitor patients closely for symptoms and signs that may be clinical manifestations of underlying imAEs. Patients with suspected imAEs should be thoroughly evaluated to rule out any alternative etiologies (e.g., disease progression, concomitant medications, infections). In the absence of a clear alternative etiology, all such events should be managed as if they were immune-mediated. Institute medical management promptly, including specialty consultation as appropriate. In general, withhold study drug/study regimen for severe (Grade 3) imAEs. Permanently discontinue study drug/study regimen for life-threatening (Grade 4) imAEs, recurrent severe (Grade 3) imAEs that require systemic immunosuppressive treatment, or an inability to reduce corticosteroid dose to 10 mg or less of prednisone or equivalent per day within 12 weeks of initiating corticosteroids.

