Based on the severity of the imAE, durvalumab should be withheld and corticosteroids administered. Upon improvement to Grade ≤ 1 , corticosteroid should be tapered over ≥ 28 days. More potent immunosuppressive agents such as TNF inhibitors (e.g., infliximab) should be considered for events not responding to systemic steroids. Alternative immunosuppressive agents not listed in this guideline may be considered at the discretion of the investigator based on clinical practice and relevant guidelines. With long-term steroid and other immunosuppressive use, consider need for *Pneumocystis jirovecii* pneumonia (PJP, formerly known as *Pneumocystis carinii* pneumonia) prophylaxis, gastrointestinal protection, and glucose monitoring.

Dose modifications of study drug/study regimen should be based on severity of treatment-emergent toxicities graded per NCI CTCAE version in the applicable study protocol.

Relevant Society Guidelines for Management of imAEs

These society guidelines are provided as references to serve in support of best clinical practice and the TMGs. Please note, these were the current versions of these guidelines at the time of updating TMGs. Please refer to the most up to date version of these guidelines.

1. Brahmer JR, et al. Society for Immunotherapy of Cancer (SITC) clinical practice guideline on immune checkpoint inhibitor-related adverse events. J Immunother Cancer 2021;9:e002435
2. Brahmer JR, et al. Management of immune-related adverse events in patients treated with immune checkpoint inhibitor therapy: American Society of Clinical Oncology Clinical Practice Guideline. J Clin Oncol 2018;36(17):1714-1768.
3. Haanen JBag, et al. Management of toxicities for immunotherapy: European Society for Medical Oncology (ESMO) clinical practice guidelines for diagnosis, treatment, and follow-up. Annals Oncol 2017;28(Suppl4):i119-i1142.
4. Sangro B, et al. Diagnosis and management of toxicities of immune checkpoint inhibitors in hepatocellular carcinoma. J Hepatol 2020;72(2):320-341.
- 1.5. Thompson JA, et al. National Comprehensive Cancer Network Guidelines: Management of immunotherapy-related toxicities version 3.2021. Published May 14, 2021.

| Specific Immune-Mediated Reactions | | | |
|--|---|---------------------------|--|
| | Grade of the Event (NCI CTCAE version 4.03) | Dose Modifications | Toxicity Management |

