| Nephritis or Renal Dysfunction (Elevated Serum Creatinine) | 
Any Grade (Refer to NCI CTCAE applicable version in study protocol for defining the CTCAE grade/severity)
 | General Guidance | 
For Any Grade:
 
 - Consult a Nephrologist - Monitor for signs and symptoms that may be related to changes in renal function (e.g. routine urinalysis, elevated serum BUN and creatinine, decreased creatinine clearance, electrolyte imbalance, decrease in urine output, proteinuria, etc.) - Patients should be thoroughly evaluated to rule out any alternative etiology (e.g., disease progression, infections. Recent IV contrast, medications, fluid status) - Consider using steroids in the absence of clear alternative etiology even for low grade events (Grade 2), in order to prevent potential progression to higher grade events. |

| | | | |
|--|----------------|--|---|
| | Grade 1 | No dose modification | 
For Grade 1:
 
 - Monitor serum creatinine weekly and any accompanying symptom 
 • If creatinine returns to baseline, resume its regular monitoring per study protocol. • If it worsens, depending on the severity, treat as Grade 2 or Grade 3 or 4 - Consider symptomatic treatment including hydration, electrolyte replacement, diuretics, etc. |
| | Grade 2 | 
Hold study drug/study regimen until resolution to \leq Grade 1 or baseline
 
 • • If toxicity improves to \leq Grade 1 or baseline then resume study drug/study regimen after completion of steroid taper (<10mg prednisone or equivalent) | 
For Grade 2:
 
 - Consider symptomatic treatment including hydration, electrolyte replacement, diuretics, etc. - Carefully monitor serum creatinine every 2-3 days and as clinically warranted - Consult Nephrologist and consider renal biopsy if clinically indicated - If event is persistent beyond > 3-5 days or worsens, promptly start prednisone 1 to 2 mg/kg/day or IV equivalent - If event is not responsive within 3-5 days or worsens despite prednisone at 1-2 mg/kg/day or IV equivalent, consider additional workup When event returns to baseline, resume study drug/study regimen and routine serum creatinine monitoring per study protocol. |

| | | | |
|--|---|--|--|

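### Appendix B, Grade 2 nephritis: the dose cell requires a completed steroid taper before durvalumab restarts, while the management cell of the same row restarts at baseline with no steroid condition

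*Combined protocol and SAP*

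**What the plan says.** Section 6.1 sends dose modification to Appendix B: "subsequent administration of durvalumab can be modified based on toxicities observed as described in the Dosing Modification and Toxicity Management Guidelines". In Appendix B, the Grade 2 row for nephritis or renal dysfunction speaks about restart in two cells.

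- **Dose Modifications.** Hold until Grade 1 or lower, or baseline. The restart rule then reads: "Grade 1 or baseline then resume study drug/study regimen after completion of steroid taper (<10mg prednisone or equivalent").
- **Toxicity Management.** Check creatinine every 2-3 days and consult a nephrologist. Then: "If event is persistent beyond > 3-5 days or worsens, promptly start prednisone 1 to 2 mg/kg/day or IV equivalent". The cell ends: "When event returns to baseline, resume study drug/study regimen and routine serum creatinine monitoring per study protocol".

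The general text of Appendix B says that, on improvement to Grade 1 or lower, "corticosteroid should be tapered over" at least 28 days. The same introduction describes the guidelines as a recommendation and points investigators to society guidelines as well.

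**The concern.** The management cell foresees a patient on high-dose prednisone and then gives a restart instruction that ignores the prednisone. A site that follows that line as written could give durvalumab while the patient is still on treatment-dose steroids for an immune-mediated event. A site that follows the dose cell would wait for the taper to finish. Two sites, each following a stated line of the protocol, would treat the same patient differently. The row can apply to any dose after the first: the second pre-operative dose and the 12 post-operative doses, so 1 + 12 = 13 per patient.

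**Working it through.** The protocol states no figure to reproduce here. The check compares the texts and then sizes the gap.

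**1. The two cells side by side**

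| State of the patient | Dose cell | Management cell |
|---|---|---|
| Baseline, no steroids given | restart | restart |
| Baseline, taper complete | restart | restart |
| Baseline, still on 10 mg or more | hold | restart |

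The third line is the conflict. For a patient at Grade 1 but not yet at baseline, the management cell is silent. It says what to do on return to baseline and does not forbid an earlier restart.

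**2. Does any other text decide between the cells?**

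- Section 6.1 refers to Appendix B and ranks neither column above the other.
- Section 7.1.11 says "Steroids should be considered in the absence of clear alternative etiology even for low grade events (Grade 2") and points on to Table 1. It gives no restart rule.
- The Appendix B introduction lists "inability to reduce corticosteroid dose to 10 mg or less of prednisone or equivalent per day within 12 weeks of initiating corticosteroids" as a reason for permanent discontinuation. That limits how long steroids may last; it does not say when dosing may resume.
- The taper of at least 28 days is not linked to restart.
- Section 6.2.4, item 4, does not block dosing on prednisone: "Use of immunosuppressive medications for the management of investigational product-related AEs or in subjects with contrast allergies is acceptable".

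None of these settles the point.

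**3. Is the sentence deliberate?** At Grade 2, the rows for pneumonitis, colitis, hepatitis, pancreatitis and rash, and the catch-all row for other immune-mediated reactions, put the restart rule in the dose column with a taper condition. Nephritis is the only Grade 2 row whose management cell also tells the site to resume study drug. Its own Grade 1 row, on return to baseline, restores monitoring only. This looks like a drafting slip.

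**4. Size of the gap.** Let G be the day the event reaches Grade 1 or lower (the taper starts), B the day it reaches baseline (B is G or later), and T the taper length (at least 28 days).

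- Management cell: earliest restart is B.
- Dose cell: earliest restart is the later of B and G + T.
- Gap = T − (B − G), or zero if that is negative.

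With T = 28 and B − G assumed to be 0, 14 or 28 days, the gap is 28, 14 or 0 days. A longer taper adds to it. If passing below 10 mg counts as completing the taper, a linear 28-day taper (assumed) reaches 10 mg after 28 × (1 − 10/75) = 24.3 days from 75 mg, or 28 × (1 − 10/150) = 26.1 days from 150 mg. With B = G, the gap is then about 24 to 26 days. Post-operative doses are 4 weeks (28 days) apart, so at 28 days the gap equals one dose interval.

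**5. Steroid dose at stake.** At the 75 kg average weight in the fixed-dosing rationale (Section 2.2.5), 1 to 2 mg/kg/day is 75 to 150 mg/day, or 75/10 = 7.5 to 150/10 = 15 times the cut-off. This is the upper case, because a patient who reached Grade 1 before baseline would already be tapering.

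**6. Frequency.** Section 2.2.4 lists treatment-related events seen in at least 2% of patients in the cited durvalumab study in locally advanced or metastatic NSCLC. No renal term is listed, so each was below 2%. Carried over to 60 patients, that is fewer than 0.02 × 60 = 1.2 per term. This is only a guide: the population differs and the figure covers all grades. The conflict also needs Grade 2, prednisone started, baseline reached before the taper ends, and a dose due in that window.

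**The case against.** The best defence is that the management cell omits the taper and does not waive it. The columns are labelled, the full restart rule sits under Dose Modifications, and a site can obey both cells by waiting for baseline and for the end of the taper. The appendix is a recommendation, refers readers to society guidelines, and asks for a nephrology consult in this row. No passage shows that dosing at 10 mg or more of prednisone causes harm.

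Most of this stands, and it keeps the point small. It does not remove the conflict. The management line is a positive instruction to resume the drug, and it follows an order for high-dose prednisone in the same cell. The row does not tell the reader to combine the cells. Combining them would also tighten the dose cell, which allows restart at Grade 1 without a return to baseline. As for harm, the protocol sets the below-10 mg condition itself; the point is only that the row should apply it consistently.

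A reader might infer that the cells also clash at Grade 1 short of baseline. That needs the management sentence to mean restart only at baseline, which it does not say. A reader might also class the Grade 2 rows for neurotoxicity, neuromotor syndromes and myositis as the same error because they state no taper condition. Those rows are silent; they do not give two competing instructions.

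**Conclusion.** The inconsistency is real and confined to one situation: Grade 2 nephritis back at baseline with prednisone still at 10 mg or more. There the two cells give opposite instructions and nothing else in the protocol decides. The restart dates differ by up to the taper length, at least 28 days, if Grade 1 and baseline are reached on the same day; the difference is smaller if baseline comes later. Few patients would be affected.

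A reader might infer that this threatens the timing of surgery or the comparison of major pathological response. The documents do not support that. They give no recovery times for nephritis, and any delay from waiting for the taper comes from the dose-column rule, which should stay. No effect on the primary endpoint or on any statistical figure follows. It is a minor safety-consistency correction.

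**What to change.** In the Grade 2 nephritis row, delete the reference to study drug and study regimen from the last sentence of the Toxicity Management cell. On return to baseline, that sentence should restore routine serum creatinine monitoring only. The Dose Modifications cell then governs restart alone, as in the comparable rows, and no other row needs to change.

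The cost is one shortened sentence in the next amendment, with no added visits, tests or patients. Sites that would have restarted at baseline will give some doses later, as the dose column already requires. Restart at Grade 1 short of baseline stays allowed once any taper is complete.
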